## PROTOCOL AMENDMENT SUMMARY OF CHANGES

### DOCUMENT HISTORY

Document	Country/countries impacted by amendment	Date, version
Amended Clinical Trial protocol 04	All	25-Apr-2024, version 1 (electronic 4.0)
Amended Clinical Trial protocol 03	Czech Republic	04-Dec-2023, version 1 (electronic 3.0)
Amended Clinical Trial protocol 02	EU	22-Nov-2023, version 1 (electronic 2.0)
Amended Clinical Trial protocol 01	Japan	19-Oct-2023, version 1 (electronic 1.0)
Original Protocol	Not applicable	08-Jun-2023, version 1 (electronic 2.0)

### Amended protocol 04 (25 April 2024)

This amended protocol (amendment 04) is considered to be substantial based on the criteria set forth in Article 2(2)(13) of the Regulation of the European Parliament and the Council of the European Union.

### OVERALL RATIONALE FOR THE AMENDMENT

This amendment is implemented to unify at a global level (where possible) local country amendments made at the request of Health Authorities and to add further clarifications to the protocol.

Protocol amendment summary of changes table

Section # and Name	Description of Change	Brief Rationale
Legal registered address	The legal registered address of Sanofi-Aventis Recherche & Développement has been changed to [name].	From February 1 st , 2024, headquarter office location for the Sponsor "Sanofi-Aventis Recherche & Développement" has moved from Chilly-Mazarin to Gentilly, France.
1.1 Synopsis 3 Objectives, Endpoints and Estimands	PASI secondary endpoint clarified as "percent change from baseline" and not "change from baseline" as previously described.  sPGA secondary timepoint clarified as Week 12 and not "from baseline to Week 12".	The intended wording was "percent change", the word "percent" was omitted in error.  sPGA is not a response/change assessment, therefore analysis only required at Week 12 and not in comparison to baseline.
	sPGA exploratory timepoint clarified at Week 4 and 8 and not "from baseline to Week 4 and 8".	sPGA is not a response/change assessment, therefore analysis only required at Week 4 and 8 and not in comparison to baseline.
1.3 Schedule of activities (SoA) – footnote a 7.1 IMP Discontinuation	Clarified the assessments required when patients prematurely discontinue treatment. Further distinguished between patients who	The requirement for patients to undergo all assessments once withdrawn from treatment is deemed not necessary especially with regards to assessments directly linked with

Section # and Name	Description of Change	Brief Rationale
7.1.1 Permanent discontinuation	withdraw from IMP and those who withdraw from the study ie, consent withdrawal.	the administration of IMP such as PK, bloods etc.
3 Objectives, Endpoints and Estimands – Table 2	The word "prohibited medication" has been replaced by "concomitant medication which could have an impact on the efficacy of the IMP " to include all possible prohibited, permitted, and rescue medications.	Clarification.
9.2.2.2 Main analytical approach		
5.2 Exclusion Criteria		
5.2 Exclusion Criteria		
6.9.2 Prohibited concomitant medication	E18: Clarified that the use of 1,25-dihydroxy vitamin D3 and analogues is prohibited only when administered at high doses with the intent to treat psoriasis. Oral intake for the treatment of other indications is not restricted.	Restrictions around the intake of Vitamin D was too broad.
5.5 Re-testing Laboratory Inclusion/Exclusion criteria	Clarified that only those assessments that did not meet eligibility criteria at the initial assessment, or were performed earlier than 28 days before randomization (outside screening timelines), must be repeated at re-screening. Removed the restriction of laboratory assessments that can be repeated ie, those that are not of explicit exclusionary laboratory testing.  Removed repeated text that required consultation with the medical monitor.	Repeating all screening assessments would be an inconvenience for patients and site staff and there is no clinical justification to support this.
6.5 Study IMP compliance	Clarified in the first paragraph that "When participants are dosed at the site, the Investigator or the designee will provide IMP to the participant from a new IMP kit, and not from a previous IMP kit".  Clarified that participants would be determined compliant if they received 80% or more of their scheduled IMP during the treatment period.	Repetition.  Clarification.
6.9.3 Permitted concomitant therapy	Clarification of the text for better linguistic understanding.	Guidance provided to investigators on compliance estimations in line with Sanofi procedures.
7.1.1 Permanent discontinuation	Provided recommended wash out period for SAR441566 before starting another treatment.	Clarification of the text.
7.1.3 [REDACTED]	Clarified that the [REDACTED] will be used for the assessment of [REDACTED]. This is in line with other sections of the protocol.	Additional guidance given to investigators in case they want to start another treatment in patients who discontinue SAR441566.  Aligning text throughout the protocol.

Section # and Name	Description of Change	Brief Rationale
7.1.4 Temporary discontinuation	Clarified that temporary IMP discontinuations correspond to ≥2 consecutive IMP doses not being administered.	Provide clear guidance to investigators.
8 Study Assessments and Procedures	Corrected previous wording that allowed the use of local laboratory results to determine eligibility as long as these fell within protocol required timelines. Eligibility should be determined based on central laboratory results with specific exceptions for TB and pregnancy testing.	Incorrect process included in error.
8.4.8 Adverse events of special interest	Removed AESI relating to drug abuse with IMP. This was in error copied from the protocol template and not applicable to this study and IMP.	Included in error.
8.8 Biomarkers	This section of the study protocol stated in error that the proteomics blood sample was an optional sample. This was not in line with other sections of the protocol and ICF, which stated that the proteomics sample is mandatory.	Protocol wording inconsistency.
9.3 Interim Analysis		EoS is the last visit for these patients.
10.3.2 Definition of an SAE	Typographical error, for clarification the word "intervention" was added to the following sentence: "Medical or scientific judgment should be exercised by the Investigator in deciding whether SAE reporting is appropriate in other situations such as important medical events that may not be immediately life-threatening or result in death or hospitalization but may jeopardize the participant or may require medical or surgical intervention to prevent one of the other outcomes listed in the above definition".	Definition error.
10.13.3 Amended protocol 03 (04 December 2023) Throughout	This section has been added to the protocol amendment history. Minor editorial, typographical error corrections and document formatting revisions.	Keeping track of previous amendments. Minor, therefore, have not been summarized.

## LIST OF ABBREVIATIONS

AE:	adverse event
AESI:	adverse event of special interest
ALP:	alkaline phosphatase
ALT:	alanine aminotransferase
AST:	aspartate aminotransferase
AUC:	area under the curve
AxMP:	auxiliary medicinal product
BCG:	Bacillus-Calmette-Guérin
BID:	bis in die - twice a day
BMI:	body mass index
BSA:	body surface area
BUN:	blood urea nitrogen
CASP8:	caspase-8
CBC:	complete blood count
CIOMS:	Council for International Organizations of Medical Sciences
C max :	maximum plasma concentration
CNIL:	Commission Nationale de l'Informatique et des Libertés
CPK:	creatine phosphokinase
CRP:	C-reactive protein
CSICF:	core study informed consent form
CYP:	cytochrome P450
D1:	first day of IMP intake, baseline, randomization
DDI:	drug-drug interaction
DLQI:	dermatology life quality index
DNA:	deoxyribonucleic acid
DTP:	direct to participant
ECG:	electrocardiogram
eCRF:	electronic case report form
EFPIA:	European Federation of Pharmaceutical Industries and Associations
EoS:	end of study
EoT:	end of treatment
ETIP:	experienced targeted immunotherapy population
EU:	European Union
EUDAMED:	European database for Medical Devices

FDA:	Food and Drug Administration
FSH:	follicle stimulating hormone
GCP:	Good clinical practice
GDPR:	general data protection regulation
HBcAb:	hepatitis B core antibody
HBsAb:	hepatitis B surface antibody
HBsAg:	hepatitis B surface antigen
HBV:	hepatitis B virus

hCG:	human chorionic gonadotropin
HCV:	hepatitis C virus
HDL:	high-density lipoprotein
HIV:	human immunodeficiency virus
hsCRP:	high-sensitivity C-reactive protein
IB:	investigator's brochure
ICF:	informed consent form
ICH:	International council for harmonization of technical requirements for pharmaceuticals for human use
IDMC:	Independent data monitoring committee
IEC:	Independent Ethics Committee
IgM:	immunoglobulin
IGRA:	interferon gamma release assay
IL:	interleukin
IM:	intramuscular
IMP:	investigational medicinal product
IND:	investigational new drug
IRB:	institutional review board
ITT:	intent-to-treat
IUD:	intrauterine device
IUS:	intrauterine hormone-releasing system
IWRS:	interactive web response system
LDL:	low-density lipoprotein
LTBI:	latent tuberculosis infection
MAD:	multiple ascending dose
MCH:	mean corpuscular hemoglobin
MCP-mod:	multiple comparison procedures modelling
MCV:	mean corpuscular volume
mTNF $\alpha$ :	membrane bound tumor necrosis factor alpha
MTX:	methotrexate

NCT:	national center for tumor
NEMO:	nuclear factor kappa B essential modulator
NF- $\kappa$ B:	nuclear factor kappa B
NMPA:	National Medical Products Administration
NRS:	numeric rating scale
NTIP:	naïve targeted immunotherapy population
PASI:	psoriasis area and severity index
PCR:	polymerase chain reaction
PCSA:	potentially clinically significant abnormalities
PD:	pharmacodynamics

P-gp:	P-glycoprotein
PK:	pharmacokinetic
PMDA:	Pharmaceuticals and Medical Devices Agency

POM: proof of mechanism

PRO: patient reported outcome

QD: quaque die - once a day

QTLs: quality tolerance limits

RBC: red blood cell

RIPK-1: receptor-interacting protein kinase 1

RNA: ribonucleic acid

SAD: single ascending dose

SAE: serious adverse event

SAP: statistical analysis plan

SPGA: static psoriasis global assessment

sTNF $\alpha$ : soluble tumor necrosis factor alpha

SUSAR: suspected unexpected serious adverse reaction

t1/2z: terminal elimination half-life

TB: tuberculosis

TE: treatment-emergent

TEAE: treatment-emergent adverse event

TNF: tumor necrosis factor

TNFR1: tumor necrosis factor receptor 1

TNFR2: tumor necrosis factor receptor 2

TNF $\alpha$ : tumor necrosis factor alpha

Tregs: regulatory T-cells

ULN: upper limit of normal

WBC: white blood cell

WHO: World health organisation

Wnumber: week followed by the week number from baseline

WOCBP: woman of child-bearing potential

WONCBP: woman of non-child-bearing potential

# 1 PROTOCOL SUMMARY

## 1.1 SYNOPSIS

### Protocol title:

A Phase 2, International, Multicenter, Randomized, Double-blind, Placebo-controlled, Dose-ranging study of Efficacy and Safety of SAR441566 in Adults with Moderate to Severe Plaque Psoriasis

### Brief title:

A study to evaluate efficacy and safety of SAR441566 in adults with plaque psoriasis

### Regulatory agency identifier number(s):

IND:	166996
NCT:	NCT06073119
WHO:	U1111-1290-5787
EUDAMED:	Not applicable yet
EU trial number:	2023-503911-14

### Rationale:

Tumor necrosis factor alpha (TNF $\alpha$ ) is a cytokine with pleiotropic effects on both pathologic and homeostatic processes. In psoriasis, TNF $\alpha$  plays a key role in driving inflammation. Consequently, the inhibition of TNF $\alpha$  signaling is a frequently used therapy option in the management of psoriasis.

SAR441566 is a small molecule inhibitor of tumor necrosis factor receptor 1 (TNFR1) signaling, by changing the configuration of the soluble TNF alpha (sTNF $\alpha$ ) trimer and preventing its interaction with TNFR1. SAR441566 binds to the center of sTNF $\alpha$  resulting in an allosteric stabilization of a naturally occurring asymmetric form of the sTNF $\alpha$ , which would otherwise be transient (1, 2). Using analytical size exclusion, O'Connell et al. (1) demonstrated that this asymmetric trimer has an impaired capacity to engage with TNFR1. The authors further demonstrated that stabilizing the asymmetric sTNF $\alpha$  trimer, impairs TNFR1 signaling *in vitro*. In contrast to biologic TNF inhibitors, this small molecule appears to preserve signaling through TNFR2. TNFR2 signaling contributes to Treg expansion and function; and is crucial for host defense against a variety of pathogens. Thus, maintenance of TNFR2 function can potentially result in lower infection risks and enhanced immune homeostasis by preserving Treg cells' functionality.

The doses to be tested in this study were selected according to the assessments of preliminary safety, pharmacokinetic and pharmacodynamics of SAR441566 in former single ascending dose (SAD, TDU16919) and multiple ascending dose (MAD, TDR16920) studies, and proof of mechanism phase 1 study (PDY16918) in mild to moderate Psoriasis participants. In these first-in-human studies, SAR441566 demonstrated favorable safety, pharmacokinetic and pharmacodynamic characteristics, which supports the advancement of SAR441566 into clinical

studies in participants with moderate to severe psoriasis. The aim of this Phase 2 trial is to evaluate the efficacy, suitable dose, and safety of SAR441566 in treating plaque psoriasis.

Two populations of participants are eligible for this study:

1. Naïve targeted Immunotherapy population (NTIP): Participants naïve to biologics and small molecules to treat psoriasis. This population is the primary population for efficacy analysis, to demonstrate the superiority of SAR441566 compared to placebo in the NTIP.
2. Experienced targeted Immunotherapy population (ETIP): Participants who previously received targeted immunotherapy for psoriasis. The ETIP is for exploratory purposes only, to assess efficacy of SAR441566 compared to placebo in the ETIP.

### Objectives and endpoints:

	Objectives	Endpoints
Primary	

• To demonstrate the superiority of SAR441566 over placebo in participants with moderate to severe plaque psoriasis, in the NTIP.

	

• Proportion of participants with a 75% or greater PASI score (Psoriasis Area and Severity Index score) improvement (reduction) from baseline (PASI75) at Week 12.

Secondary	

• To evaluate the efficacy of SAR441566 in plaque psoriasis as compared to placebo in the NTIP.

• To evaluate the safety of SAR441566.

• To assess pharmacokinetics of SAR441566 in participants with moderate to severe plaque psoriasis.

	

• PASI percent change from baseline to Week 12.

• Proportion of participants with static Psoriasis Global Assessment (sPGA) score 0 (complete clearance) or 1 (minimal disease) at Week 12.

• Incidence of TEAE, SAEs, and AEs of AESIs.

• Incidence of study IMP permanent discontinuations and study withdrawals due to TEAEs.

• Participants with medically significant changes in vital signs, ECG, and/or laboratory evaluations.

• Plasma pre-dose and post-dose concentrations of SAR441566.

For China, see [Section 10.7.1](#) details.

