- k When several assessments take place at the same visit, the following order is recommended: Patient Reported Outcome Measures (Questionnaires), Triplicate ECG (after 10min of rest), Blood sampling, Urine test (when applicable), IMP administration, Vital signs, Physical examination, Clinical assessments, IMP compliance check, verification of the Medication Intake Questionnaire (paper), Prior and concomitant medications, AE reporting, IMP dispensed for home administration. And during Post-IMP PK blood sampling visits, conclude with Triplicate ECG (after 10min of rest and within 15min prior to PK blood sampling), followed by PK blood sampling.
- l Dispensed with Medication Intake Questionnaire (paper).
- m Compliance will be assessed by the investigator by direct questioning, verifying the Medication Intake Questionnaire (paper), and counting returned tablets in each pack during the site visits and documented in the source documents and relevant form. Deviations from the prescribed dosage regimen must be recorded.
- n Questionnaire provided to the trial participant on D1 and at each visit, then returned by the participant at each visit and checked by the investigator to verify the IMP intake and potential adverse events.
- o Clinical assessments should be completed by the same physician for a given participant, if possible, to secure longitudinal comparison and avoid any bias.
- p BSA will be extracted from PASI assessment ([Section 8.2.3](#)).

s Refer to [Section 5.3.2](#) for further details.

*t* Refer to Section 8.3.6 – Pregnancy testing for instruction on timepoints

v Hematology: RBC, RBC indices, hemoglobin, hematocrit, thrombocyte count (platelets), leukocyte count (white blood cell count) with differential in absolute counts (including neutrophils, eosinophils, basophils, lymphocytes (including CD4 count), monocytes).

Clinical chemistry: Sodium, potassium, chloride, bicarbonate, blood urea nitrogen (BUN), creatinine, creatinine clearance, CPK, calcium, phosphate, total protein, albumin, alanine aminotransferase (ALT), aspartate aminotransferase (AST), alkaline phosphatase (ALP), total bilirubin, conjugated bilirubin, unconjugated bilirubin, glucose (non-fasting).

w Fasting total cholesterol, fasting triglycerides, HDL, and LDL. Participant must be fasting for 8 hours prior to laboratory testing (may consume water). A light meal will be provided by the site after the laboratory tests, lipids panel and pre-dose-PK.

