### 8.3.3 Electrocardiograms

- Standard 12-lead ECGs are recorded after at least 10 minutes of rest in supine position using an electrocardiographic device. The electrodes will be positioned at the same place for each ECG recording throughout the study (eg, attachment sites of the leads will be visualized on a transparent paper).
- Triplicate 12-lead ECG will be obtained as outlined in the SoA (see [Section 1.3](#)) using an ECG machine that automatically calculates the heart rate and measures PR, QRS, QT, and QTcF intervals. [REDACTED].
- At each timepoint at which triplicate ECGs are required, 3 individual ECG tracings should be obtained within 5 minutes, with at least 1 minute between 2 replicates.
- The ECG should be recorded [REDACTED]  
[REDACTED]  
[REDACTED]  
• [REDACTED]  
[REDACTED].

- Each ECG consists of a 10-second recording of the 12 leads simultaneously, leading to:
  - A single 12-lead ECG (50 mm/s, 10 mm/mV) printout with heart rate, PR, QRS, QT, QTcF automatic correction evaluation using Fridericia formula (by the ECG device), including date, time, number of the participant, and at least 3 complexes for each lead. The Investigator should revise the results of the printout and his/hers medical opinion together with the automatic values will be recorded in the eCRF. This printout will be retained at the site. A second printout may be performed also, if needed.
  - A digital storage that enables potential further reading by an ECG central laboratory: each digital file will be identified by theoretical time (day and time Dxx Txx Hxx), real date and real time (recorder time), Sponsor study code, participant number (eg, 3 digits), and site and country numbers, if relevant. The digital recording, data storage, and transmission (whenever requested) need to comply with all applicable regulatory requirements (ie, FDA 21 code of federal regulations [CFR], Part 11).

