#### **Analyses according to PCSA**

PCSA analyses will be performed based on the PCSA list currently in effect at Sanofi at the time of the database lock.

Analyses according to PCSA will be performed based on the worst value during the treatment-emergent period, using all measurements either local or central, either scheduled, nonscheduled or repeated).

For laboratory variables, vital signs and ECG variables, the incidence of participants with at least one PCSA during the treatment-emergent period will be summarized regardless of the baseline level and according to the following baseline status categories:

- Normal/missing.
- Abnormal according to PCSA criterion or criteria.

For ECG, the incidence of participants with at least one abnormal ECG during the treatment-emergent period will be summarized regardless of the baseline level and according to the following baseline status categories:

- Normal/missing.
- Abnormal.

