3.6.3 Additional safety assessments

3.6.3.1 Laboratory variables, vital signs and electrocardiograms (ECGs)

The following laboratory variables, vital signs and electrocardiogram (ECG) variables will be analyzed. They will be converted into standard international units.

- Hematology:
 - Red blood cells and platelets and coagulation: hemoglobin, hematocrit, mean corpuscular volume, mean corpuscular hemoglobin, red blood cell count, %Reticulocytes, platelet count
 - White blood cells: white blood cell count, neutrophils, lymphocytes, monocytes, basophils, eosinophils
- Clinical chemistry:
 - Metabolism: glucose, [REDACTED] total protein, albumin, creatine phosphokinase
 - Electrolytes: sodium, potassium, chloride, calcium, calcium corrected, bicarbonate
$$\text{Calcium Corrected (mmol/L)} = \text{Total calcium (mmol/L)} + 0.8 * 0.25 * [4 - \text{Serum albumin (g/L)} * 0.1]$$
 - Renal function: creatinine, creatinine clearance, blood urea nitrogen.
Creatinine clearance will be derived with the equation of Cockcroft and Gault using weight assessed at the same visit as creatinine.
 - Liver function: alanine aminotransferase (ALT), aspartate aminotransferase (AST), alkaline phosphatase, total and direct bilirubin
 - Pregnancy test: Serum β -human chorionic gonadotropin (choriogonadotropin Beta as needed for women of childbearing potential)
- Vital signs: sitting heart rate, sitting systolic and diastolic blood pressure, temperature.
- ECG variables: heart rate, PR, QRS, QT, and corrected QTcF. The average of the triplicate ECG assessments will be used.

Data below the lower limit of quantitation/detection limit (LLOQ) will be replaced by half of the LLOQ, data above the upper limit of quantification will be replaced by ULOQ value.

Quantitative analyses

When relevant, for laboratory variables, vital signs and ECG variables above, descriptive statistics for results and changes from baseline will be provided for each planned visit, the last value and the worst value (minimum and/or maximum value depending on the parameter) during the on-treatment period. These analyses will be performed using central measurements only for laboratory variables and ECG variables.

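### The SAP drops the protocol's abnormal-ECG incidence without declaring it, has no adverse-event row for TEAE-related study withdrawals, and leaves phosphate off its visible laboratory list

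*Protocol*

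**What the plan says.** The protocol synopsis lists two relevant secondary safety endpoints, and SAP Table 1 repeats both: "Participants with medically significant changes in vital signs, ECG, and/or laboratory evaluations" and "Incidence of study IMP permanent discontinuations and study withdrawals due to TEAEs".

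**ECG.** Protocol 9.2.6.2 plans incidence by PCSA criteria for laboratory, vital-sign and ECG variables. It then adds a separate ECG analysis: "For ECG, the incidence of participants with at least one abnormal ECG during the treatment-emergent period will be summarized", split by normal/missing versus abnormal at baseline. Protocol 8.3.3 says of the investigator's review of each tracing that the "medical opinion together with the automatic values will be recorded in the eCRF". SAP 3.6.3.1 names five ECG variables (heart rate, PR, QRS, QT, QTcF) and applies PCSA incidence to them.

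**Withdrawals.** SAP 3.3 sends the adverse-event secondary endpoints to SAP 3.6.2. That section and its Table 6 cover TEAEs leading to permanent IMP discontinuation and to death. SAP 5.2 (disposition) counts study non-completers by main reason and treats adverse event as one of the reasons.

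**Laboratory.** Footnote v of the protocol schedule requires phosphate within chemistry ("creatinine clearance, CPK, calcium, phosphate, total protein, albumin"), and Protocol Table 7 also lists it. The SAP's line reads "Electrolytes: sodium, potassium, chloride, calcium, calcium corrected, bicarbonate". Footnote v also places CD4 in hematology ("lymphocytes (including CD4 count), monocytes"), whereas Table 7 puts it beside HIV serology under screening tests.

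**The concern.** A table that the protocol plans, and one half of a stated secondary endpoint, should each have a named analysis in the SAP, or the SAP should say they were removed. Neither is done here.

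The ECG omission matters most. Rate and interval thresholds do not describe rhythm or waveform. That information sits in the investigator's reading, which is collected but not tabulated. The protocol itself treats cardiac safety with care: a personal or family history of long QT syndrome and a QTcF above 450 ms are both exclusions.

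For withdrawals, IMP discontinuation is not a substitute. Protocol 7.1.1 lets a participant stop IMP and stay on study, so the two counts can differ.

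For phosphate, the SAP's PCSA analysis refers back to the variables listed above it. A test that is not on the list gets neither the PCSA incidence nor descriptive statistics.

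**Working it through.** The plan states no figure to reproduce, so the check is a side-by-side comparison with one upper bound.

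**1. Abnormal ECG**
- Planned in Protocol 9.2.6.2: (a) ECG PCSA incidence; (b) any abnormal ECG, by baseline status.
- In SAP 3.6.3.1: (a) is present; (b) is absent.
- In SAP 3.9: two changes are listed, the wording of an exploratory PASI endpoint and the cancelled interim analysis. The removal of (b) is not among them.
- Data available: triplicate ECGs are scheduled at all seven visits, and the investigator's opinion is entered in the eCRF.

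**2. Study withdrawal due to a TEAE**
- Endpoint: two components, IMP discontinuation and study withdrawal, each due to a TEAE.
- SAP 3.6.2 and Table 6: the first component only.
- SAP 5.2 captures the second component indirectly, and differs from the endpoint in three ways:
  - It assigns one main reason per participant, so a withdrawal to which an adverse event contributed can fall under another reason.
  - It is not limited to TEAEs. The treatment-emergent period ends 5 days after the last dose (SAP 3.1), while follow-up runs 4 weeks, or 2 weeks for those enrolled under older protocol versions. An adverse event behind a withdrawal in follow-up may therefore not be treatment-emergent.
  - It is not stated to use the safety population.
- The gap begins in the protocol: Protocol 9.2.6.1 also plans a table only for TEAEs leading to permanent treatment discontinuation.

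**3. Phosphate**
- Required by schedule footnote v and Table 7. It is not in the SAP electrolyte line, which has no redaction.
- The SAP metabolism line is partly redacted. SAP 3.6.3.1 later plots cholesterol and triglycerides, which are also missing from the visible list, so the redaction may hold lipids. Absence of phosphate is therefore established for the visible text only.
- Upper bound on scheduled post-baseline values in the treatment period (Weeks 2, 4, 8 and 12): 207 participants × 4 visits = 828. The true number would be lower, because participants who stop IMP early have no further laboratory tests after their end-of-treatment visit.

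**4. CD4 count**
- Footnote v reads as a repeated hematology test; Table 7 reads as a screening test. The eligibility use in exclusion E 29 fits the second reading. The two protocol passages disagree, and the SAP's white-cell list ("White blood cells: white blood cell count, neutrophils, lymphocytes, monocytes, basophils, eosinophils") is consistent with screening only.

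**The case against.** The strongest reply is that these endpoints are largely covered.

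- The endpoint on medically significant changes carries no threshold, and PCSA incidence by baseline status, with a normal-range fallback, is a reasonable way to analyse it.
- Protocol 8.3.4 requires clinically significant laboratory changes to be recorded as adverse events, and Protocol 10.3.1 counts clinically significant ECG findings as adverse events. Both then reach the TEAE tables.
- Withdrawals for an adverse event are visible in disposition.
- SAP section 1 says that 3.9 describes major changes, and one descriptive table may not be major.
- Safety analysis is descriptive, with no testing.

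Most of this stands, and it limits the point. A reader might infer that these endpoints have no analysis at all, or that such changes could never surface. The documents do not support that, for the reasons just given. A reader might also infer that CD4 is a safety measure left unanalysed. That cannot be shown: Table 7 suggests a screening test, Protocol 10.7.1 lists CD4 among exploratory immune-cell biomarkers, and a bullet in SAP 3.7.1.3 is redacted.

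Three things remain. The adverse-event route depends on the investigator judging a finding clinically significant, which is narrower than any abnormal ECG. The disposition table is not the endpoint as worded, and SAP 3.3 does not point to it. Phosphate has no listed place.

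**Conclusion.** The point holds as a modest completeness gap. One protocol-planned safety table is dropped without being recorded, one component of a secondary endpoint has no row in the section assigned to it, and one required chemistry test is missing from the visible list. The withdrawal gap is shared with the protocol and is not purely an SAP omission.

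The only size the documents support is the ceiling of 828 scheduled on-treatment phosphate values. Counting all seven laboratory visits would wrongly include screening, baseline and follow-up. A reader might also want a number of hidden withdrawals. The documents do not give one: the SAP's 10% dropout is stated for the NTIP, not for all 207, and no share due to TEAEs is given.

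The conclusion rests on two assumptions: that phosphate is not in the redacted part of the metabolism line, and that the protocol's abnormal-ECG category refers to the investigator's reading, which 9.2.6.2 does not state. No efficacy conclusion is affected.

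**What to change.** - **SAP 3.6.3.1, ECG:** restore the table of participants with any treatment-emergent abnormal ECG by baseline status (normal/missing, abnormal), and name the investigator's reading in the eCRF as its source. If the sponsor prefers not to produce it, record the removal and the reason in SAP 3.9.
- **SAP 3.6.3.1, laboratory:** add phosphate to the electrolytes. The normal-range fallback applies if it has no PCSA criterion.
- **SAP 3.6.2 overview and Table 6:** add a row for TEAEs leading to study withdrawal, in the safety population.
- **CD4:** reconcile schedule footnote v with Table 7. Nothing more is needed in the SAP unless CD4 proves to be a repeated post-baseline test.

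The cost is SAP wording and a few descriptive tables from data already collected. The withdrawal row assumes that the eCRF can link a study withdrawal to an adverse-event record. Only the alignment of footnote v with Table 7 touches the protocol.
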